### **Continuous outcomes such as Self-efficacy:**

Repeated-measures analyses for self-efficacy will be performed with a means model via the SAS MIXED Procedure (version 9.4; SAS Institute, Cary, NC), providing separate estimates of the means by time on study (at 5 scheduled assessments) and intervention group. The model will include three predictors (intervention arm, time on study and the statistical interaction between intervention arm and time on study). A compound-symmetric variance-covariance form in repeated measurements will be assumed for self-efficacy and robust estimates of the standard errors of parameters will be used to perform statistical tests and construct 95% confidence intervals. The model-based means are unbiased with unbalanced and missing

data, so long as the missing data are non-informative (missing at random, MAR). A P value  $\leq 0.05$  will be considered statistically significant for the main effects (intervention and time on study) and for the intervention by time on study interaction effect from the repeated measures analysis. **The statistical test for interaction between time on study and intervention will be the primary overall hypothesis test to determine whether self-efficacy in the two intervention groups changed in significantly different ways during follow-up (i.e., different temporal patterns over time).** If mean self-efficacy in the two intervention groups is consistently different or similar over time (i.e., no statistical interaction) then the main effect test for intervention will be used as the primary test of intervention efficacy. If a significant interaction is detected then t-tests will be used to compare the differences between the model-based intervention means at each time point and to compare differences over time within each intervention arm. Specific statistical tests will be done within the framework of the mixed effects linear model. All statistical tests will be 2-sided and unadjusted for multiple comparisons. The same analysis plan described above will be used for the other outcomes that are continuous (i.e., willingness to use PrEP).

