### 2.4 Study Hypotheses/Research Questions

- *Relative to the control condition, YMSM exposed to the GC intervention will report significantly greater increases in routine HIV/STI testing over a 12-month period. HIV testing will be the primary outcome for the trial.*
- *Relative to the control condition, YMSM exposed to the GC intervention will report increases in motivation around HIV testing (conceptualized as HIV/STI testing intentions, self-efficacy to engage in HIV/STI testing, and overcoming testing-related barriers).*
- *Relative to the control condition, YMSM exposed to the GC intervention will report significantly greater PrEP awareness and willingness to use PrEP).*

The primary analyses of the data from the Get Connected 2-parallel group randomized clinical trial will be performed according to the participants' original treatment assignment (i.e., intention-

to-treat analyses) and the inclusion of all data from all participants randomized in the final analysis.

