## 6.0 EVALUATIONS AND MEASURES

### 6.1 Behavioral Evaluations

#### 6.1.1 Pre-intervention (Baseline) Evaluations/Measures

- *Socio-demographic information:* We will include questions on race/ethnicity, educational attainment, employment status, housing status, and history of incarceration, sexual identity, and “outness” to their social network.
- *HIV Testing:* The baseline survey will include questions on HIV testing history.
- *STI Testing:* At baseline, we will assess STI testing history and knowledge about STIs. We will ask participants what STIs they have been tested for, the date of their most recent STI test (if known), and whether a medical provider has ever diagnosed them with an STI.
- *Mechanisms of Change:* We will assess YMSM’s psychosocial correlates predicted to adopt HIV services (i.e., Attitudes, Norms, Self-Efficacy, and Behavioral Intentions to get HIV tested). Integrated Behavioral Model constructs will be assessed with 3 subscales assessing YMSM’s attitudes, social norms, and behavioral intentions that we have used in the past with this population. Each attitude item is measured with three five-

point semantic differential scales (good-bad; worthless-valuable; pleasant-unpleasant). Social norms assess the extent to which participants felt that friends and family believed he should test for HIV on a 1 to 5 scale. Behavioral intentions items assess participants' intention to adopt HIV testing, on a 1 (very unlikely) to 5 (very likely) scale. Self-efficacy to access HIV/STI services and to discuss sexuality-related issues with provider will be ascertained, as well as YMSM's perceived confidence of visiting a testing site or requesting a home kit.

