- Sexual Risk Behavior:* Sexual risk behavior will be assessed using the Sexual Practices Assessment Schedule used in previous online studies with YMSM to explore the number of occasions of different sexual acts (oral, anal; receptive, insertive) with three different types of partners (romantic interest, casual partner “hookup,” or friend with benefits), use of condoms during the past 3 months, and knowledge about partners' HIV status and PrEP use. Assessments ascertain sexual behaviors with male and female partners, and will be asked at each follow-up. At-risk sex will be defined as any anal intercourse without condoms and/or PrEP that occurs with a person of known positive or unknown sero-status. We will assess the number of partners with whom participants had “at-risk sex.”
- PrEP Awareness and Willingness:* The survey will contain a brief description of PrEP to orient the participant. Questions are adapted from recent studies of PrEP attitudes with YMSM. PrEP awareness will be a single item measure of whether the participant has heard of PrEP (yes/no/I don't know). PrEP willingness will be measured with an existing 8-item scale developed for YMSM to gauge likelihood of PrEP use across different conditions (e.g., partner types; experiencing potential side effects).
- Technology and Social Media Use:* Given the online interface of the intervention, we will include Pew Internet Survey questions regarding use of different devices, the number of hours spent online through each device, the reasons for social media use, sites commonly frequented, and extent to which the Internet supplements face-to-face interactions. We will also measure AMSM's frequency of use of social media to look for HIV or sexual health-related information, and their online partner-seeking behaviors

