## 10.2 Power Estimates

10.2.1 The primary outcomes for the proposed trial are HIV-negative and HIV-unknown YMSM's successful uptake of HIV and STI testing willingness (e.g., HIV/STI testing), and PrEP awareness and willingness. For HIV testing, we define power as correctly identifying the difference in the proportion of YMSM who engage in HIV testing 2 or more times at least 3 months apart in the 12-month follow-up period ("frequent tester") in our treatment arm (GC) vs. our attention-control arm. For STI testing, we define it as receiving at least one STI test during the 12-month follow-up period. For proportions (e.g., HIV testing; PrEP awareness), our sample size calculations are based on a two-sample test of proportions using a two-sided significance level of 0.05. In order to have 80% power to compare GC to the attention-control group, we require at least 400 participants to find an absolute difference of 13% in cross-sectional analyses. Assuming within-person correlation of 0.25, we can detect an 8.8% difference. A less favorable within-person correlation of 0.75 allows us to detect an 11.3% difference.

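### The section 2.4 model for continuous outcomes leaves out the baseline score that the trial collects and conflicts with section 10.3.1; adjusting for it would sharpen the arm comparison at no cost

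*Combined protocol and SAP*

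**What the plan says.** Section 2.4, under continuous outcomes, describes a SAS MIXED means model for self-efficacy, "providing separate estimates of the means by time on study (at 5 scheduled assessments) and intervention group". Its terms are listed in full: "The model will include three predictors (intervention arm, time on study and the statistical interaction between intervention arm and time on study". The covariance form is compound symmetric with robust standard errors, and the same plan is extended to willingness to use PrEP. The five assessments are months 1, 3, 6, 9 and 12 (study abstract; section 2.4, binary outcomes).

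The arm-by-time interaction is the first-ranked test. If there is no interaction, the arm main effect becomes the efficacy test. If there is one, the arms are compared by t-tests at each time point.

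Section 6.1.1 lists both scores among the baseline measures: "PrEP willingness will be measured with an existing 8-item scale developed for YMSM", and "Self-efficacy to access HIV/STI services and to discuss sexuality-related issues with provider will be ascertained".

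Three other places bear on baseline:

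- Section 10.1 describes adjusted regressions. The covariates are socio-demographics, substance use, psychological distress and process data. The outcome's own baseline is not among them.
- Section 10.3.1 describes a mixed model with an identity link for continuous outcomes, a covariate term whose content is not listed, and baseline plus four follow-ups as the response times.
- Section 10.3.1 adjusts explicitly for baseline values only in a collapsed logistic analysis of some binary outcomes.

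**The concern.** The hypothesis in section 2.4 is that participants in the intervention arm "will report increases in motivation around HIV testing", relative to control. A model of the five follow-ups alone has no pre-intervention value in it. The comparison of arms remains valid because of randomization, but stable differences between people that the baseline survey has already measured stay in the error term.

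What is at stake is precision on PrEP willingness, which section 3.1 lists among the primary outcomes, and on the continuous mechanism measures such as self-efficacy. The second problem is that sections 2.4 and 10.3.1 give two models for the same outcomes, with different visits and a different role for baseline. An analyst following the document could defend either after seeing the data.

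**Working it through.** **The plan's own figure.** Section 10.2 gives power for proportions only, set at 80% and tested "using a two-sided significance level of 0.05". Its sample size statement is: "we require at least 400 participants to find an absolute difference of 13% in cross-sectional analyses". The control rate is not stated. With an assumed 25% against 38% and pooled variance under the null:

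n per arm = [1.96 × √(2 × 0.315 × 0.685) + 0.8416 × √(0.25 × 0.75 + 0.38 × 0.62)]² / 0.13² = (1.2876 + 0.5474)² / 0.0169 = 199.2, so 200 per arm and 400 in total.

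The figure is reproduced at that rate (and at 62% against 75%); at 30% the total would be 430. There is no corresponding figure for a continuous outcome to reproduce.

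**Inputs for the baseline question.**

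- Five follow-ups, compound symmetry, 1:1 allocation: from the documents.
- Within-person correlation r of 0.25 and 0.75: stated in section 10.2 for proportions. Using them for these scales is an assumption; 0.50 is the midpoint.
- The same r between baseline and every follow-up, and equal variance at baseline: assumptions. Section 2.4 assumes compound symmetry for the repeated measurements that it models, which do not include baseline.
- 200 per arm: from the 400 in section 10.2.

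**Arm difference averaged over five visits**, in units of 2 × SD² / n:

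- follow-ups only: (1 + 4r) / 5
- adjusted for baseline: (1 + 4r) / 5 − r²
- share removed: 5r² / (1 + 4r)

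| r | Follow-ups only | Adjusted | Variance removed | Detectable effect at 80% power, unadjusted to adjusted (SD) |
|---|---|---|---|---|
| 0.25 | 0.40 | 0.34 | 15.6% | 0.177 to 0.163 |
| 0.50 | 0.60 | 0.35 | 41.7% | 0.217 to 0.166 |
| 0.75 | 0.80 | 0.24 | 70.3% | 0.251 to 0.137 |

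The detectable effect is 2.8016 × √(2V / 200), where V is the unrounded table entry. For r = 0.25: 2.8016 × √(0.80 / 200) = 0.177. Put the other way, a main effect with 80% power unadjusted would have about 86%, 96% and more than 99% power adjusted.

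**Single visit.** The variance falls by r²: 6.25%, 25% and 56.25%.

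**Arm-by-time interaction among the five follow-ups.** Each follow-up has covariance r with baseline, so adjustment subtracts the same quantity, r², from every entry of the follow-up covariance matrix. That quantity cancels in any difference between visits. The reduction is 0% at every r.

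**Section 10.3.1 as written.** If time is categorical and the arms have free baseline means, the averaged arm contrast is a change from baseline. With four follow-ups its variance is (1 − r)(1 + 1/4) = 0.94, 0.63 and 0.31. Follow-ups only give (1 + 3r) / 4 = 0.44, 0.63 and 0.81. Baseline as a covariate gives (1 + 3r) / 4 − r² = 0.38, 0.38 and 0.25. On that reading 10.3.1 is less precise than covariate adjustment throughout, and at r = 0.25 less precise than ignoring baseline. If time is fitted as a slope, these formulas do not apply.

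**The case against.** The strongest objection is that the largest percentages belong to a test that section 2.4 does not rank first. That is correct. A reader might infer that the first-ranked test loses up to 70% of its variance reduction; under the plan's own covariance form the arm-by-time test gains nothing. What remains is that both routes section 2.4 then takes to an efficacy conclusion do gain: the main effect when there is no interaction, and the per-visit comparisons when there is one. An effect present by month 1 and sustained gives no interaction, so it would be judged by the main effect.

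Second, the correlation range is borrowed. The documents give no correlation, standard deviation or effect size for self-efficacy or PrEP willingness. This stands, and the percentages are conditional on it. The direction is the same for any r above zero, but at r = 0.10 the averaged gain is only 3.6%.

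Third, a reader might infer bias or an underpowered trial. The documents support neither. Randomization protects the comparison, section 2.4 names HIV testing, a binary outcome, as the trial's primary outcome, and section 10.2 makes no power claim for a continuous outcome.

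Fourth, the baseline survey is completed after randomization (study abstract; section 5.1). It precedes access to the WebApp, and section 3.4 intends participants to be blinded, so the score is usable as a covariate. But someone could be randomized and have no score, and a covariate model would then drop that person, against the section 2.4 commitment to include everyone randomized. That has to be handled.

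Finally, it is tempting to extend the point to PrEP awareness. The two-sided Z-test for independent proportions in section 2.4 cannot take a covariate, and no gain has been calculated for that outcome. The extension is not made here.

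**Conclusion.** The point holds as a free improvement in precision, together with an inconsistency that needs resolving. Section 2.4 omits a baseline score that the trial collects, section 10.1 does not restore it, and section 10.3.1 uses it only as a response in a conflicting model. Adjustment would remove about 16% to 70% of the variance of the five-visit mean arm difference and 6% to 56% of that of a single-visit difference. Both ranges assume compound symmetry extended to baseline, r from 0.25 to 0.75, and the same scale at baseline and follow-up. The first-ranked interaction test is unaffected, the planned comparison is unbiased, and no power statement in the plan fails.

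**What to change.** State one governing model for continuous outcomes and bring sections 2.4 and 10.3.1 into line with it, including the number of follow-ups. In that model:

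- keep the five follow-ups as the responses;
- add the participant's baseline score on the same scale, and its interaction with time, as covariates;
- keep randomized participants without a baseline score in the analysis, for example by a simple imputation of the baseline covariate made without reference to arm;
- confirm that the follow-up surveys repeat the same items, since section 5.4.1 says only that many baseline questions are repeated.

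The cost is a short revision of two sections, made before any unblinded analysis. It needs no new data, visits or participants.

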## 2.0 STUDY OBJECTIVES

As part of the U19 project, we propose to test the efficacy of Get Connected (GC) for increasing HIV-negative or sero-status unaware YMSM's successful uptake of HIV and STI testing willingness (HIV and STI testing). Given the overall low level of PrEP awareness and use among YMSM currently, we also include awareness of and willingness to use PrEP as a primary outcome (PrEP uptake during the trial will be measured as a secondary outcome). At the agency level, HIV/STI testing sites listed in GC will receive biannual performance assessments based on ratings that YMSM provide after visiting their locations. We will examine improvements in the quality of HIV test counseling and PrEP-related referrals to YMSM accessing local HIV/STI testing sites in the 3 cities selected to test GC.

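### For continuous outcomes, the claim of unbiased means under MAR also needs the assumed compound-symmetric covariance to be right; an unstructured covariance removes that dependence at almost no cost

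*Combined protocol and SAP*

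**What the plan says.** Section 2.4, under the heading on continuous outcomes, fits a means model in SAS MIXED with arm, time and arm-by-time as predictors over the five scheduled follow-up assessments. On the covariance: "A compound-symmetric variance-covariance form in repeated measurements will be assumed for self-efficacy". On inference: "robust estimates of the standard errors of parameters will be used to perform statistical tests and construct 95% confidence intervals". On missing data it says "The model-based means are unbiased with unbalanced and missing", with the condition "data, so long as the missing data are non-informative (missing at random, MAR".

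The arm-by-time interaction is the primary overall test. If there is no interaction, the arm main effect is tested. Visit-specific comparisons follow only after a significant interaction.

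The plan extends to PrEP willingness: "The same analysis plan described above will be used for the other outcomes that are continuous (i.e., willingness to use PrEP". Section 2.0 says "we also include awareness of and willingness to use PrEP as a primary outcome", and sections 3.1 and 10.2.1 agree. Section 2.4, however, states "HIV testing will be the primary outcome for the trial".

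Follow-up surveys are at months 1, 3, 6, 9 and 12 (section 7.3.3). Attrition is projected at 20% (section 3.1). Section 10.3.1 describes a random-intercept model, an exploratory random slope and comparison by AIC and BIC. It does not tie these to the model in section 2.4.

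**The concern.** A likelihood model handles MAR dropout by, in effect, predicting unobserved later visits from earlier ones through the fitted covariance. If that covariance is wrong, the predictions and hence the late-visit means are wrong. Robust standard errors correct the estimated variance but leave the means where they are.

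Compound symmetry gives months 1 and 12 the same correlation as months 9 and 12. For an attitude or confidence scale over a year, correlation that weakens with lag is at least as plausible.

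The plan's own treatment of binary outcomes shows the gap. There it uses GEE with an exchangeable correlation and claims unbiasedness only under MCAR. With an identity link and given variance parameters, the compound-symmetric model solves the same form of equation for the means. What lifts the claim from MCAR to MAR is a correct covariance, and section 2.4 does not say so.

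At stake are the late-visit arm contrasts, the within-arm changes over time and, in principle, the interaction test.

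**Working it through.** **The plan's own figure.** There is none to reproduce. The sizing in section 10.2.1 is for proportions only; no power or precision is given for a continuous outcome.

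**Inputs from the documents.** Visits at months 1, 3, 6, 9 and 12; 1:1 allocation with 240 per arm (section 5.3); 20% attrition (section 3.1); compound symmetry, robust standard errors and arm-by-time means (section 2.4); two-sided 5% tests.

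**Assumptions not in the documents.** Outcome SD of 1. Monotone MAR dropout, logistic on the last observed value, with slopes of 0.7 to 1.0 log-odds per SD. True correlation either compound-symmetric, or decaying with lag (0.5 or 0.75 at 3 months), or a random intercept plus decay.

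**Why the covariance matters.** Take exponential decay with 0.5 at 3 months. The months 9-12 correlation is 0.50 and the months 1-12 correlation is 0.5^(11/3) = 0.08. The compound-symmetric fit settles on one value, about 0.345.

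- A participant seen only at month 1, 1 SD above the mean, is predicted 0.345 SD above at month 12. The true expectation is 0.08.
- A participant seen through month 9, 1 SD above at month 9 and average before, is predicted 0.345/(1 + 3 × 0.345) = 0.17 SD above. The true expectation is 0.50.

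These errors have opposite signs.

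**Large-sample error at month 12** (no true effect, 20% dropout, 400,000 per arm, absolute values in SD):

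| True correlation | Dropout | Contrast error, compound symmetry |
|---|---|---|
| Compound-symmetric | any pattern | within 0.005 |
| Decaying, or intercept plus decay | same in both arms | within 0.006 |
| Decaying, or intercept plus decay | outcome-related in one arm only | 0.010 to 0.020 |
| Decaying, or intercept plus decay | opposite directions by arm | 0.023 to 0.054 |

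Unstructured covariance on the same data stays within 0.006 of the truth in every case. The individual arm means at month 12 are off by 0.016 to 0.028 under pure decay and by 0.008 to 0.016 with a random intercept plus decay, even where the contrast is not. A separate run with 60,000 per arm gave contrast errors of 0.013 and 0.022 (one arm) and 0.035 and 0.053 (opposite directions). Unstructured covariance was within 0.007.

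**By visit.** In the most adverse case (0.5 at 3 months, opposite slopes of 1.0), the contrast errors at months 1, 3, 6, 9 and 12 are 0.002, 0.030, 0.005, -0.025 and -0.054. Their average is -0.042/5 = -0.008, so the main effect is almost untouched.

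**Scale.** With 200 per arm retained, the standard error of a contrast is about sqrt(2/200) = 0.10 SD. For a stand-alone test with bias b in standard-error units, the two-sided error is P(Z > 1.96 - b) + P(Z < -1.96 - b). This gives 5.1% at b = 0.1, 5.5% at 0.2 and 7.9% at 0.5.

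**Simulated type I error** (240 per arm, sandwich standard errors, 600 trials per row, simulation error sqrt(0.05 × 0.95/600) = 0.9 points; decay is 0.5 at 3 months, slopes 1.0):

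| True correlation | Dropout | Interaction | Main effect | Month 12 alone |
|---|---|---|---|---|
| Compound-symmetric | 20%, opposite | 4.2% | 5.2% | 4.3% |
| Decaying | 20%, same | 5.2% | 5.5% | 4.3% |
| Decaying | 20%, opposite | 5.7% | 4.8% | 7.0% |
| Intercept plus decay | 20%, opposite | 4.7% | 4.8% | 4.5% |
| Decaying | 40%, opposite | 14.2% | 5.3% | 16.5% |
| Intercept plus decay | 40%, opposite | 7.8% | 4.7% | 8.3% |

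The 40% rows are a stress test, twice the projected attrition.

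**The case against.** The strongest reply is that this barely touches the tests actually planned. The primary test is the interaction, and its 5.7% in the adverse case lies within simulation error of 5%. The month-12 comparison is made only after a significant interaction, so the 7% for a stand-alone test is not an error rate of the planned procedure. That stands.

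The adverse case is also demanding. Surveys are the same in both arms (section 5.4.1), section 8.2 describes no arm-specific payment, and section 3.4 intends to blind participants. Section 3.1 calls 20% conservative, and keeping 400 of 480 means 80/480 = 16.7% loss. This too stands. Still, the arms receive different content and only the intervention site is retailored after each survey, so some difference in dropout cannot be excluded.

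A reader might infer that the plan's statement is simply false. The text does not support that: compound symmetry is declared as an assumption in the sentence before, and under it the claim is true. What is missing is the explicit condition.

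A reader might also blame the unequal visit spacing. Spacing does not cause the bias; decaying correlation breaks compound symmetry with equal spacing too.

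Finally, section 10.3.1 may be said to cover this. Its random intercept implies the same compound symmetry for a continuous outcome. The random slope would relax it, but is exploratory and not linked to section 2.4. The missing-data rules in section 10.4 do not address covariance.

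**Conclusion.** The point holds as a small, avoidable weakness. Unbiasedness under MAR in section 2.4 is conditional on compound symmetry, and the robust standard errors do not remove that condition. Under decaying correlation and about 20% MAR dropout, the month-12 contrast shifts by about 0.01 to 0.02 SD if dropout depends on the outcome in one arm only, and by up to about 0.05 SD if it runs in opposite directions. It does not shift if dropout acts alike in both arms. Under MCAR the means are unbiased with any working covariance.

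These sizes rest on assumed correlation patterns and dropout slopes, and they grow with heavier arm-specific dropout.

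A reader might infer that the trial's primary result is exposed. The documents do not support that without qualification. PrEP willingness is listed as primary in three places, but section 2.4 names HIV testing as the trial's primary outcome, and that is binary and not analysed by this model.

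**What to change.** In section 2.4, under continuous outcomes:

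1. Specify an unstructured covariance for the five follow-up visits in SAS MIXED.
2. Keep the robust standard errors.
3. Name compound symmetry as the fallback, to be used only if the unstructured model does not converge.
4. Amend the missing-data sentence to say that validity under MAR also requires an adequate covariance model.

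The cost is one option in the model statement and one or two sentences. Five visits give 5 × 6/2 = 15 covariance parameters, which 400 to 480 participants support comfortably. The design, sample size and data collection do not change.
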